16.7. Inhibitor Formation Data

16.7.1. Analysis Population

The Safety Population (as defined in Section 16.6.1) will be the basis for analyses of inhibitor formation.

16.7.2. Methods of Analysis

The proportion of subjects with inhibitors during rFVIII Fc administration will be provided with the exact (Clopper-Pearson) 2-sided, 95% confidence interval. Any subject with an inhibitor following the initial rFVIII Fc administration will be counted in the numerator; however, only subjects who have completed at least 50 EDs and 100 EDs from their initial rFVIII Fc administration will be included in the denominator. Unless all subjects complete at least 50 EDs, the proportion of subjects with inhibitors will also be calculated using all subjects, regardless of the amount of exposure to rFVIII Fc, in the denominator.

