In addition, a Phase 3 study in previously treated subjects age 12 years or older with severe hemophilia A has recently been completed (Study 997HA301). A total of 164 subjects (including 13 subjects aged 12 to 17 years) in the Phase 3 study received at least 1 dose of rFVIII Fc. This included 146 subjects treated for at least 26 weeks and 23 subjects treated for at least 39 weeks, for a total of 102.05 person-years on study.

Compared with Advate, rFVIII Fc demonstrated improved PK activity, as indicated by a 53% longer $t_{1/2}$, a 56% increase in systemic exposure, and a 36% reduction in CL, with comparable C_{max} and recovery (one-stage aPTT clotting assay).

rFVIII Fc was well tolerated in the Phase 3 study. No subject developed an inhibitor to rFVIII Fc. Common AEs observed were consistent with those expected in patients with hemophilia A. Adverse drug reactions were mild and manageable, and the majority were not treatment limiting. One nonserious event of rash required discontinuation of treatment and resolved. There was no Grade 2 or greater allergic reactions or serious vascular thrombotic events. No treatment-related serious adverse events (SAEs) were observed.

Study 8HA02PED (referred to as the pediatric study) is an open-label, multicenter study evaluating the safety, PK, and efficacy of rFVIII Fc in previously treated pediatric patients with severe hemophilia A, who are <12 years of age, and have at least 50 EDs to FVIII products prior to enrollment. Approximately 50 male subjects (25 subjects <6 years of age and 25 subjects 6 to <12 years of age) are planned to complete at least 26 weeks of prophylactic treatment to attain at least 50 EDs. At least 24 of these subjects (12 subjects <6 years of age and 12 subjects 6 to <12 years of age) will undergo an evaluation of the PK profile of pre-study FVIII and rFVIII Fc. Subjects who complete this study will be offered enrollment into the extension trial described in this protocol.

For further details regarding the clinical studies conducted with rFVIII Fc, please refer to the rFVIII Fc Investigator's Brochure.

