8.2. Exclusion Criteria

Candidates will be excluded from study entry if any of the following exclusion criteria exist at the time of signing the informed consent at Visit 1 of the study, or at the EOT of the previous study:

1. Confirmed high-titer inhibitor (≥ 5.00 BU/mL), as defined in Section 7.1.2.
2. Current enrollment in any other study.
3. Inability to comply with study requirements.
4. Other unspecified reasons that, in the opinion of the Investigator or Biogen Idec, make the subject unsuitable for enrollment.

CONFIDENTIAL

The information contained herein may not be used, disclosed, or published without the written consent of Biogen Idec MA Inc.

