16. STATISTICAL METHODS AND DETERMINATION OF SAMPLE SIZE

In general, the data for subjects who enroll from parent studies will be integrated with their data from 8HA01EXT. A parent study is defined as a study where subjects may be enrolled into 8HA01EXT after study completion or at a time specified in the protocol.

All statistical analyses will be descriptive in nature. No formal comparison is planned and no hypothesis will be formally tested. Continuous variables will be summarized and presented by number, mean, median, standard deviation, minimum and maximum, and where appropriate, with the 25th and 75th percentiles. Categorical variables will be summarized by the number and percentage in each category.

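### The 50- and 100-exposure-day inhibitor proportions count parent-study exposure, but if only rollovers are analysed, a high-titer inhibitor from that exposure has almost no route into the numerator

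*Protocol*

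**What the plan says.** - **Denominator (Protocol 16.7.2):** "only subjects who have completed at least 50 EDs and 100 EDs from their initial rFVIII Fc administration will be included in the denominator". For a rollover, the clock starts at the first parent-study dose.
- **Numerator (same section):** "Any subject with an inhibitor following the initial rFVIII Fc administration will be counted in the numerator". No minimum number of exposure days (EDs) applies.
- **Interval and second denominator (same section):** the proportion "will be provided with the exact (Clopper-Pearson) 2-sided, 95% confidence interval", and "Unless all subjects complete at least 50 EDs, the proportion of subjects with inhibitors will also be calculated using all subjects".
- **Whose data (Protocol 16):** in general, "the data for subjects who enroll from parent studies will be integrated with their data from 8HA01EXT". Protocol 16.6.1 defines the Safety Population by one dose of rFVIIIFc without naming the study. SAP 4 and 4.3 are explicit: the subjects are those who enrolled in 8HA01EXT and were dosed in it.
- **Entry:** Protocol 8.1 requires completion of a parent study. Protocol 8.2 excludes "Confirmed high-titer inhibitor (≥ 5.00 BU/mL), as defined in Section 7.1.2".
- **Endpoint (Protocol 7.1.2):** any confirmed inhibitor of at least 0.6 BU/mL, so low-titer inhibitors count too.
- **SAP:** Section 1 limits the analysis to 8HA01EXT data. Sections 8.1 and 8.3.2 plan a listing of inhibitor results, with no proportion, interval or ED denominator.

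**The concern.** The exposure clock and the entry rules refer to different moments. Exposure is counted from the first parent-study dose, but a subject becomes a rollover only after finishing that study without a confirmed high-titer inhibitor. In a rollover-only analysis, a subject who developed such an inhibitor in a parent study appears in neither numerator nor denominator. Subjects who stayed free of one bring all their parent-study EDs with them. The early window of the from-first-dose proportion is therefore selected on the outcome, at least for high-titer cases.

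Inhibitor development is the only primary endpoint. A proportion tied to 50 or 100 EDs from first dose, with an exact interval, is easily read as risk from first exposure, and nothing in Protocol 16.7.2 says that entry was conditional. With so few events expected, one missing case separates none observed from one observed. The all-subject denominator does not help, because a subject who never enrolled is missing from it as well.

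**Working it through.** **1. Planned size.** The documents state no inhibitor rate or precision target, so the only figure to reproduce is the number of subjects: 144 + 50 = 194 (Protocol 16.10), and 144 + 50 + 12 + 8 = 214 (SAP 3.3.1). Both match.

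**2. How much parent exposure is credited.** Protocol 5.1.3 says that 8HA02PED subjects are "planned to complete at least 26 weeks of prophylactic treatment to attain at least 50 EDs". EDs in 26 weeks (182 days) = 182 / dosing interval:

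| Schedule | EDs in 26 weeks |
|---|---|
| every 3 days | 182/3 = 60.7 |
| twice weekly | 182/3.5 = 52 |
| every 5 days | 182/5 = 36.4 |
| weekly | 182/7 = 26 |

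By design, 8HA02PED completers reach 50 EDs before the extension can observe them. In 997HA301 the picture is mixed. Protocol 5.1.3 gives 102.05 person-years over 164 subjects, so mean follow-up is 102.05/164 × 365.25 = 227 days, or about 45 EDs at every 5 days and 32 at weekly dosing.

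**3. Effect of missing high-titer cases.** Let m be the number of high-titer subjects who did not roll over. The documents give 0 for 997HA301 (no inhibitors among 164 dosed). For 8HA02PED, 997HA307 and 997HA309 they give no count, so m from 0 to 3 is an assumption. Further assumptions are that all m cases come from the 50 pediatric subjects, that everyone else rolls over without an inhibitor, and that all rollovers reach the ED milestone.

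For 0 cases in n, the exact upper limit is 1 − 0.025^(1/n). Otherwise the limits are the 2.5% quantile of Beta(x, n − x + 1) and the 97.5% quantile of Beta(x + 1, n − x).

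| m | Rollovers only (upper limit) | All dosed, total 194 |
|---|---|---|
| 0 | 0/194 (1.88%) | 0/194 (upper limit 1.88%) |
| 1 | 0/193 (1.89%) | 1/194 = 0.52% (0.01% to 2.84%) |
| 2 | 0/192 (1.90%) | 2/194 = 1.03% (0.13% to 3.67%) |
| 3 | 0/191 (1.91%) | 3/194 = 1.55% (0.32% to 4.45%) |

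Pediatric stratum with m = 1: 0/49 (upper limit 7.25%) instead of 1/50 = 2.00% (0.05% to 10.65%).

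**4. The opposing effect.** Cases count at any ED, but the denominator holds only subjects who reach the milestone. Take one counted case among 194 and assume that 90% or 80% reach 50 EDs: 1/175 = 0.57% or 1/155 = 0.65%, against 1/194 = 0.52% over all subjects. This raises the rate.

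**The case against.** **The population may already be right.** Protocol 16.7.1 uses the Safety Population, which 16.6.1 defines without reference to 8HA01EXT, and 16.6.2 integrates extension data with the parent studies. Read literally, this could include parent-study subjects who never enrolled. That stands as an ambiguity. The general rule in Protocol 16 points to enrollees only, and the SAP says so outright.

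**The rate is not planned in the SAP.** The restriction is explicit only in the SAP, which never computes this proportion. That is correct, and its absence for the primary endpoint is itself a gap. The proportion remains a protocol commitment, and copying 16.7.2 unchanged into the SAP would bring the problem with it.

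**The endpoint is broader than high titer.** Low-titer inhibitors are not excluded at entry, and one that arose in a parent study counts if the subject rolls over. This stands and confines the point to high-titer cases. A high-titer case is also not strictly impossible: a first positive near parent end of treatment, unconfirmed at entry, could be confirmed afterwards. In the other direction, the completion requirement may remove low-titer subjects who left a parent study early.

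**A tempting stronger reading.** A reader might infer that the rate is biased toward zero and its limits too favourable. The documents do not support that. No missing case is documented, 997HA301 supplies 144 of the 194 planned subjects (74%) and had no inhibitors, and the numerator rule pushes the rate up. That upward push cannot restore a missing case, however: with no case among rollovers, the estimate stays at zero whatever the denominator.

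**Most subjects reaching 50 EDs before entry.** This too might be inferred, but it is supported only for 8HA02PED. 997HA301 had an episodic arm and long-interval schedules, and some 997HA307 and 997HA309 subjects had only PK injections (SAP 5.1.1).

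**Conclusion.** The point holds as a structural risk. Under Protocol 16.7.2 with a rollover-only population, parent-study EDs enter the denominator with almost no chance of yielding a high-titer case, so the proportion can understate high-titer risk from first exposure.

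Its size depends on a count that the documents do not give. If no high-titer subject was lost before rollover, nothing changes. Each lost case is worth about 0.5 percentage points overall and 2 points within 8HA02PED, and the first one replaces a zero with an observed event. Because the numerator rule works in the opposite direction, the net direction for the whole endpoint is not fixed. The conclusion assumes that the analysis is restricted to rollovers. The study is descriptive, so the harm would be a misread rate rather than a wrong test. It deserves correction because it concerns the only primary endpoint, and the plan should not rely on the unreported counts being zero.

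**What to change.** 1. In Protocol 16.7.2, name the population, and say whether dosed parent-study subjects who did not enroll are included.
2. Compute the 50- and 100-ED proportions from first dose in all rFVIIIFc-dosed parent-study subjects, whether or not they enrolled.
3. For a rollover-only analysis, count EDs and new cases from 8HA01EXT entry, and label the result as conditional on no confirmed high-titer inhibitor at entry.
4. Put every numerator case in its denominator: subjects who reach the milestone, plus any case that arose before it.
5. Carry the corrected proportion and its exact interval into SAP 8.1 and 8.3.2, and add the exception to the 8HA01EXT-only scope in SAP 1 that step 2 needs.

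The cost is wording and some extra programming. The parent-study inhibitor and ED data should already be with the sponsor, since the protocol plans to integrate parent-study data. The reported rate may become less favourable. No visit, sample or treatment rule changes.

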6.2. Endpoints

6.2.1. Primary Endpoint

The primary endpoint is the occurrence of inhibitor development

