Treatment will be administered as tailored prophylaxis, weekly prophylaxis, personalized prophylaxis, or as an on-demand regimen. Subjects 12 years of age or older will be able to switch from one regimen to another at scheduled or unscheduled visits during the study, per Investigator discretion. Subjects less than 12 years of age will receive 1 of 2 prophylactic regimens, tailored or personalized, and will not have the option to change to a weekly prophylactic or on-demand regimen, unless they reach the age of 12 years during the study, at which time they can use any of the 4 treatment regimens.

To ensure accuracy of FVIII trough/peak (recovery) and inhibitor testing, subjects following a prophylaxis regimen should schedule clinic visits 48 hours after the previous dose of rFVIII Fc, whenever possible.

CONFIDENTIAL

The information contained herein may not be used, disclosed, or published without the written consent of Biogen Idec MA Inc.

Subjects first dosed with rFVIII Fc when <12 years of age will be followed to at least 100 EDs, even if rFVIII Fc becomes commercially available.

All subjects will have the opportunity to continue in this study for up to 4 years or until rFVIII Fc is commercially available in the applicable participating country.

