11. WITHDRAWAL OF SUBJECTS FROM STUDY TREATMENT AND/OR THE STUDY

11.1. Discontinuation of Study Treatment

A subject *must* permanently discontinue rFVIII Fc for any of the following reasons:

- A Grade 2 or greater allergic drug reaction in association with administration of rFVIII Fc, as defined below by the Recommendations for Grading of Acute and Sub-Acute Toxic Effects on the World Health Organization WHO scale [[WHO handbook, 1979](#)]:
 - Grade 2 Bronchospasm related to rFVIII Fc; no parenteral therapy needed
 - Grade 3 Bronchospasm related to rFVIII Fc; parenteral therapy required
 - Grade 4 Anaphylaxis related to rFVIII Fc
- A high-titer inhibitor (≥ 5.00 BU/mL), as defined in Section 7.1.2.
- Use of FVIII products other than rFVIII Fc, unless it occurs in 1 life-threatening emergency and/or as a result of 1 accidental use, and the Sponsor agrees to retain the subject in the study. Use must be recorded in the subject's eDiary and eCRF and the investigator should contact the Sponsor Medical Monitor.
- Any condition a subject develops that precludes him from complying with the study procedures.
- The subject experiences a medical emergency that necessitates discontinuation of treatment.
- Clinical judgment of the Investigator: a subject may have treatment permanently discontinued, if in the opinion of the Investigator, it is not in the subject's best interest to continue with the study treatment.
- The parent or legal guardian can withdraw the subject from the study at will at any time.
- The subject and/or his parent/guardian withdraw consent.
- At the discretion of the Investigator or Sponsor for noncompliance.

The reason for discontinuation of study treatment must be recorded in the subject's eCRF.

For any subject who no longer responds to treatment with rFVIII Fc, as determined by the Investigator, a decision will be made with the Sponsor whether to continue the subject on the study.

Subjects who discontinue treatment should remain in the study to complete protocol-required tests and assessments, and then must be permanently withdrawn from the study.

CONFIDENTIAL

The information contained herein may not be used, disclosed, or published without the written consent of Biogen Idec MA Inc.

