16.6. Safety

16.6.1. Analysis Population

The Safety Population will include all subjects with at least 1 dose of rFVIII Fc.

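### The 50-ED and 100-ED inhibitor proportions put every case in the numerator but only milestone completers in the denominator, so the exact interval does not apply and the figures run high

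*Protocol*

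**What the plan says.** Protocol 6.2.1 names one primary endpoint: "The primary endpoint is the occurrence of inhibitor development". Protocol 16.7.2 is the only place that plans an estimate for it, a proportion with an "exact (Clopper-Pearson) 2-sided, 95% confidence interval". The numerator rule is "Any subject with an inhibitor following the initial rFVIII Fc administration will be counted in the numerator". The denominator rule is that "only subjects who have completed at least 50 EDs and 100 EDs from their initial rFVIII Fc administration will be included in the denominator". I read this as two proportions, one per milestone. No clause adds a case that falls short of the milestone to the denominator.

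The same section adds that, if anyone falls short of the lower milestone, "the proportion of subjects with inhibitors will also be calculated using all subjects, regardless of the amount of exposure to rFVIII Fc, in the denominator". The population is the one in Protocol 16.6.1: "The Safety Population will include all subjects with at least 1 dose of rFVIII Fc".

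Protocol 11.1 lists among the reasons for permanent discontinuation "A high-titer inhibitor (≥ 5.00 BU/mL), as defined in Section 7.1.2". A lower-titer confirmed inhibitor is not on that list. Participation runs "for up to 4 years or until rFVIII Fc is commercially available in the applicable participating country" (Protocol 7.1), but the same section requires that those first dosed under 12 years of age be followed to at least 100 EDs even after launch.

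The SAP does not carry the calculation forward. Sections 8.1 and 8.3.2 define and list inhibitor results, the table list has no inhibitor proportion, and the SAP Introduction restricts the analysis to 8HA01EXT data.

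**The concern.** There are three defects in the milestone figures.

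1. **The numerator is not nested in the denominator.** A subject who develops a high-titer inhibitor before the milestone stops accruing EDs. He counts above the line and can never count below it. Clopper-Pearson limits assume x successes among n subjects, and that is not what this ratio is.
2. **The exclusion of early leavers is one-sided in its effect.** A subject who stops short of the milestone still adds to the numerator if he had an inhibitor. If he had none, he contributes nothing, not even the inhibitor-free exposure he accrued. The ratio is therefore biased upward, by more as the share leaving early grows.
3. **The numerator has no ED cap.** A case at ED 300 would count in the 50-ED figure, so that figure is not a risk by 50 EDs.

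The all-subjects proportion is nested, and Clopper-Pearson applies to it. But it treats any short exposure as complete follow-up, so as an estimate of risk by a milestone it errs low. It is also triggered only by the 50-ED condition. It does not repair the milestone figures. What is at stake is whether the reported inhibitor risk can be interpreted as a risk by a stated exposure, and compared across analyses with different amounts of early leaving.

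**Working it through.** **Inputs from the documents.** N = 144 + 50 = 194 (Protocol 16.10, which reproduces the planned total). The SAP total is 144 + 50 + 12 + 8 = 214 (SAP 3.3.1). Three high-titer cases is the stopping number (Protocol 7.3). The documents give no expected inhibitor rate, interval width or share of subjects missing a milestone, so there is no planned figure for this estimate to reproduce.

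**Step 1: nesting alone.** Take 3 cases, all stopping before the milestone, with everyone else reaching it.
- As written: 3/(194 − 3) = 3/191 = 1.57%, Clopper-Pearson 0.33 to 4.52%.
- Nested: 3/194 = 1.55%, 0.32 to 4.45%.

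The change is trivial at this N.

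**Step 2: adding inhibitor-free early leavers.** Assume also that 30% of the 191 inhibitor-free subjects (57) miss the milestone.
- As written: 3/(191 − 57) = 3/134 = 2.24% (0.46 to 6.40%).
- Cases added to the denominator: 3/137 = 2.19% (0.45 to 6.27%).

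Nearly all of the shift from 1.55% comes from dropping the 57, and nesting recovers little of it.

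**Step 3: bias against a defined risk.** Assumptions: true risk by 100 EDs is 3%; constant hazard, so λ = −ln(0.97)/100 per ED; a share q leaves, spread evenly over 0 to 100 EDs, independently of inhibitor risk; the numerator is limited to cases by 100 EDs, which is kinder than the protocol's rule.
- Average risk among leavers: E = 1 − 0.03/0.030459 = 0.01508.
- Cases per subject: C = 0.03(1 − q) + qE.
- As written, all cases stop: C / [0.97(1 − q)].
- As written, all cases continue dosing until they leave: C / (1 − q).
- Nested denominator: C / [(1 − q) + qE].
- All subjects: C / 1.

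For q = 30%, C = 0.021 + 0.004523 = 0.025523. The four results are 0.025523/0.679 = 3.76%, 0.025523/0.7 = 3.65%, 0.025523/0.704523 = 3.62%, and 2.55%. Relative to the true 3%:

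| Share leaving early | As written, all cases stop | As written, all cases continue | Nested denominator | All subjects |
|---|---|---|---|---|
| 10% | +9% | +6% | +5% | −5% |
| 20% | +16% | +13% | +12% | −10% |
| 30% | +25% | +22% | +21% | −15% |

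**Step 4: interval coverage.** Simulated trials (20,000 per setting, N = 194, every case stopping before the milestone, true risk 3%) gave coverage of the nominal 95% interval of 95.7% with 10% of inhibitor-free subjects missing the milestone, 87.1% with 30% and 69.0% with 50%. At a true risk of 1% the figures were 98.4%, 95.4% and 86.9%. Nearly all misses had the lower limit above the true risk.

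**Step 5: zero cases.** The estimate is 0% under every rule. Only the upper limit moves: 1.88% for 0/194, 2.09% for 0/175 and 2.68% for 0/136.

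**The case against.** The case for leaving the rule alone has several parts.

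- **The plan already reports a coherent figure.** This stands in part: the all-subjects proportion is nested and would be given whenever anyone misses 50 EDs. A reader might infer that the protocol provides no valid inhibitor proportion at all, and that would be wrong. But this figure answers a different question and leaves the milestone figures as they are.
- **Early leaving may be small.** This stands as a limit on size. Entrants have completed a parent study, and EDs count from the first rFVIIIFc dose. The pediatric study aims at 50 EDs or more, and 146 of 164 subjects in 997HA301 were treated for at least 26 weeks (Protocol 5.1.3). About 50 of the 194 planned subjects come from the pediatric study and are covered by the 100-ED follow-up requirement. Weekly dosing gives about 52 EDs a year, so it reaches 100 EDs in about two years. It is tempting to infer that commercial launch or weekly dosing will remove a large share before the milestone; the documents do not support that.
- **Not every case stops.** Correct. Only high-titer inhibitors force discontinuation, hence the second column of the table.
- **No case may occur.** None did in 997HA301 (0/164; exact upper limit 2.2%, over shorter exposure). Then the point estimate is unaffected. A rule still has to work when cases arise, and the stopping rule contemplates three.
- **The bias is conservative and all analyses are descriptive.** The direction is upward, so nobody should read this as flattering the product. An interval centred too high, by an amount that depends on early leaving, is still hard to interpret.

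**Conclusion.** The point holds as a defect in a stated rule for the sole primary endpoint. The milestone ratios are not binomial proportions whenever a case stops short of the milestone, Clopper-Pearson is not valid for them, the numerator is not limited to the milestone, and excluding inhibitor-free early leavers biases the figures upward.

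The size is uncertain and may be small. Nesting alone is worth 0.02 percentage points at 3 cases in 194. The 9% to 25% range (6% to 22% if all cases continue) rests on an assumed 3% risk by 100 EDs, constant hazard and 10% to 30% leaving evenly over 0 to 100 EDs, none of which is in the documents. The coverage losses in Step 4 also assume that every case stops early. A reader might take these figures as the expected error in this trial; they only show how the error grows with early leaving.

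Because the SAP plans only listings on 8HA01EXT data, the rule is neither corrected nor restated there, and the final analysis plan contains no inhibitor proportion.

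**What to change.** In Protocol 16.7.2:

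- **(a)** Define each milestone denominator as subjects who reached that milestone or had an inhibitor by it. Limit the numerator to cases by that milestone. Apply Clopper-Pearson to this nested set and label it conservative, since the table shows that most of the upward bias remains.
- **(b)** Add cumulative incidence on the ED scale at 50 and 100 EDs: 1 minus Kaplan-Meier, EDs counted from the first rFVIIIFc dose, censored at the last ED with a valid inhibitor test. This uses early leavers for the exposure they had and removes their bias if leaving is unrelated to inhibitor risk. Name an interval method that still gives an upper limit with no events; a Greenwood interval would collapse to zero width.
- **(c)** Keep the all-subjects proportion, and report later cases as a count per exposure.

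In SAP 8.1 and 8.3.2, add this calculation and its table, with EDs and cases integrated from the parent studies, as an explicit exception to the restriction to 8HA01EXT data.

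Cost: one extra table, the work of integrating parent-study exposure and inhibitor data, and milestone estimates that change slightly and will usually be lower.
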